Patients randomized to the pharmacologic VTE prophylaxis arm will receive a dose of subcutaneous heparin 5,000 units within 2 hours prior to incision, and subcutaneous heparin 5,000 units every 8 hours after surgery until discharge. Total number of doses received and missed doses will be recorded. No post-discharge pharmacologic prophylaxis will be prescribed. Per routine care, patients will be requested to inform their urologist's office if they experience any symptoms of DVT or PE, or any other concerns, during the first 30 days after surgery. All patients will receive a phone call around 30 days after surgery to assess primary outcomes including documentation of whether they experienced a postoperative VTE episode and any treatment initiated for confirmed VTE. Any patient endorsing symptoms concerning for VTE up to 30 days after surgery will be recommended to undergo urgent evaluation and care, locally or at Johns Hopkins, with imaging/evaluation results forwarded to Johns Hopkins. Patients and their insurance will be responsible for the costs as part of routine care. The 30-day phone call will be the only planned, study-initiated contact after surgery with the patient to evaluate symptomatic outcomes and will be the same for both the control and pharmacologic prophylaxis arms.

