The primary efficacy outcome will be the incidence of symptomatic VTE. The primary safety outcomes will include three separate measures of incidence of symptomatic lymphocele, incidence of symptomatic hematoma, or major bleeding within 30 days after surgery. The secondary outcomes (all regarded separately) will be estimated blood loss from surgery, total surgical drain output after surgery (for patients with surgical drains), the overall incidence of VTE (asymptomatic or symptomatic) determined from the subcohort undergoing lower extremity Duplex screening ultrasound, and surveillance bias (measured by use of postoperative diagnostic imaging, either as inpatient or within 30 days from surgery). Two planned interim analyses will be conducted as outlined in the study statistics section with early stopping rules due to adverse events or demonstrated futility.

[figure not shown]

Figure 1. Diagram of plan for stratified randomization of patients to arms and outcomes assessed.

b. Study duration and number of study visits required of research participants.

The study protocol will be largely implemented during routine visits required of all RP patients (described above) with the addition of a visit specifically for screening lower extremity Duplex for eligible patients as part of the run-in described above. Patients will be contacted by phone around 30 days after surgery to tabulate the primary and secondary outcomes. Patients may initiate contact before this point if they wish to report concerns or diagnosis of VTE. Any events that occur after 30 days and are reported by patients in an unsolicited fashion will be documented, but they will not be included as part of the primary outcome. There will be no planned contact initiated by the study team with patients after 30 days except to confirm documentation of VTE events that occurred up to 30 days from surgery due to symptoms or discovered on screening lower extremity Duplex ultrasound. Patients reporting symptoms concerning for VTE at or before the 30 day mark who are diagnosed within 2 weeks of reporting symptoms (even if after the 30 day mark) will be included as symptomatic VTE events for the primary outcome.

c. Blinding, including justification for blinding or not blinding the trial, if applicable.

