The secondary outcomes (all regarded separately) will be estimated blood loss from surgery, total surgical drain output after surgery (for patients with surgical drains), the overall incidence of VTE (asymptomatic or symptomatic) determined from the subcohort undergoing lower extremity Duplex screening ultrasound, and surveillance bias (measured by use of postoperative diagnostic imaging). Estimated blood loss will be recorded from the anesthesia data report from surgery. Total surgical drain output will be recorded based on ins and outs flowsheets routinely recorded by nurses when emptying drains. Surveillance bias will be determined by recording the type and frequency of postoperative imaging performed while a patient is in the hospital or within 30 days of surgery after discharge.

The overall rate of VTE will only be determined for patients in the subcohort. The asymptomatic VTE will be determined based on the results of the screening lower extremity Duplex ultrasound for asymptomatic DVTs. The overall rate of VTE will be determined by adding the number of asymptomatic VTE events to the number of symptomatic VTE events experienced in the subcohort.

d. Statistical plan including sample size justification and interim data analyses.

Pharmacologic VTE prophylaxis can be expected to prevent between 67% to 75% of DVTs [33]. Given the lowest expected primary outcome event rate will be for VTE, the trial sample size will be based on a power of 80% ($\beta=0.2$) and one-sided α of 0.05 for prevention of post-operative VTE with pharmacologic prophylaxis reducing the rate from 5% to 1.5%. Including two interim analyses of the primary endpoint as outlined in the Interim Analyses section below, the total sample size needed will be 666 (333 per treatment arm) based on 2000 simulations for 82% power (exact α -spending and futility boundaries are outlined below). As mentioned above, the primary efficacy analysis will compare symptomatic VTE rates at the 30-day follow-up for all patients. Secondary analyses will be conducted to compare secondary outcomes between treatment arms at the completion of the study as well. It is expected that during full-time patient enrollment, the study would require about 2 years to accrue patients assuming 50% enrollment.

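### The surveillance-bias imaging count closes at day 30, but a primary VTE can be diagnosed up to 2 weeks after a symptom report made by day 30, so some qualifying work-ups fall outside the check

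*Combined protocol and SAP*

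**What the plan says.** All references are to the combined protocol and SAP.

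- **Imaging count.** Section 7c: "Surveillance bias will be determined by recording the type and frequency of postoperative imaging performed while a patient is in the hospital or within 30" (in days, counted from surgery). Section 4a gives the same limit: "measured by use of postoperative diagnostic imaging, either as inpatient or within 30 days from surgery". Section 7d compares the number of imaging tests between arms by t-test or Wilcoxon test. Aim 8 in section 2 states the purpose, which is to see whether VTE imaging relative to symptoms differs by arm.
- **Primary outcome.** Section 7b requires imaging confirmation after a symptom-prompted evaluation, except for deaths attributed to VTE. Section 4b extends this for patients who report symptoms at or before day 30: those "diagnosed within 2 weeks of reporting symptoms (even if after the 30 day mark) will be included as symptomatic VTE events for the primary outcome". Section 7b does not repeat this extension.
- **The call.** Section 4a: "All patients will receive a phone call around 30 days after surgery to assess primary outcomes". It adds that "The 30-day phone call will be the only planned, study-initiated contact after surgery with the patient to evaluate symptomatic outcomes", and that "Any patient endorsing symptoms concerning for VTE up to 30 days after surgery will be recommended to undergo urgent evaluation and care", with results forwarded to the study centre.
- **After day 30.** Section 4b plans no study-initiated contact except to confirm VTE events that occurred by day 30.
- **Blinding.** Section 4c: heparin is unblinded after surgery and controls receive no placebo.

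**The concern.** Nearly every primary event needs a scan, so the VTE comparison depends on who is sent for imaging. After surgery the trial is open, and patients and treating staff can know the arm. The imaging count is there so that a reader can judge whether the arms were worked up alike. For that, it should cover the scans that can produce a primary event.

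As written it does not cover all of them. Section 4b extends the endpoint for diagnoses that come after day 30, but neither statement of the imaging window is extended with it. The part left out lies close to the one contact at which every patient is asked about symptoms. If work-up differed by arm in that stretch, the count could look balanced while some primary events came from imaging it never recorded. Negative scans matter as much as positive ones here, because they show how readily each arm was tested.

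**Working it through.** **1. The plan's own figure.** Inputs from section 7d: 5% against 1.5%, one-sided alpha 0.05, 333 per arm, 82% power. With pooled variance and no continuity correction,

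n = [z(α)·√(2p̄q̄) + z(power)·√(p₁q₁ + p₂q₂)]² / (p₁ − p₂)², where p̄ = 0.0325.

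- At 82% power: n = (1.645 × 0.2508 + 0.915 × 0.2496)² / 0.035² ≈ 335.3, so 336 per arm and 672 in total. This is 0.9% above the stated 666.
- Power at 333 per arm is 81.8% for a fixed design.
- A three-look simulation (111, 222 and 333 per arm; nominal efficacy p of 0.001, 0.015 and 0.048; interim futility p of 0.816 and 0.272) gives 82.5%.

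The stated design is reproduced, and the imaging window plays no part in it.

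**2. The two windows.** Let r be the day of the symptom report, with r ≤ 30 (section 4b). The latest qualifying diagnosis is day r + 14. The imaging count ends at day 30 (sections 4a and 7c). The uncounted stretch is therefore (r + 14) − 30 = r − 16 days when r exceeds 16, and zero otherwise.

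| Report day | Latest qualifying diagnosis | Days outside the count |
|---|---|---|
| 16 | 30 | 0 |
| 28 | 42 | 12 |
| 30 | 44 | 14 |

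The gap exists only for reports made after day 16 and imaged after day 30. For example, a DVT found on day 34 after a day-30 report is a primary event, but the scan that found it is not counted. A negative scan on day 34 from the same kind of report is not counted either.

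**3. How many events this could touch.** Planned events are 333 × 0.05 = 16.65 (control) and 333 × 0.015 = 4.995 (heparin), a total of 21.645 and a difference of 11.655. The documents do not give the share of events diagnosed after day 30, so it is taken as an assumption, equal in both arms:

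| Assumed share | Control | Heparin | Total | Part of the planned difference |
|---|---|---|---|---|
| 0% | 0 | 0 | 0 | 0 |
| 5% | 0.83 | 0.25 | 1.08 | 0.58 |
| 10% | 1.67 | 0.50 | 2.16 | 1.17 |
| 20% | 3.33 | 1.00 | 4.33 | 2.33 |
| 30% | 5.00 | 1.50 | 6.49 | 3.50 |

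The last column is the ordinary proportional share of a true effect. It is not an estimate of bias. The number of uncounted negative scans cannot be derived, because no ratio of scans to events is given.

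**The case against.** The other side has several sound points.

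- **The call is only around day 30.** Imaging after a slightly earlier call may still be counted. A symptom first reported at a later call is not clearly within the section 4b rule, so a VTE found then may not qualify at all. A reader might infer that everything the call triggers is lost to the check; the documents do not support that. What stands is the narrower case of symptoms reported by day 30 and imaged afterwards.
- **The late share may be close to zero.** Patients are asked to report symptoms throughout the first 30 days, and evaluation is to be urgent. In the screening series cited in section 3, the 7 patients who presented symptomatically after a negative scan all did so within 2 weeks of surgery. That is one series and does not settle the matter, but it is why the range above starts at zero.
- **There is another check.** A subcohort of at least 200 patients, funds allowing, is offered a screening Duplex whatever their symptoms (section 4a), performed and read blinded to arm (section 4c). It covers only part of the trial, but it means the imaging count is not the sole safeguard against detection bias.
- **The call is standardised.** It is the same in both arms, with a listed set of symptoms. Differential work-up at this stage is possible, because patients know their arm, but it is not shown.
- **Late results need not be lost.** Section 4a has evaluation results forwarded without limiting this to positive ones. What is missing is a rule that puts them in the count.

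These points limit the reach of the concern. None of them aligns the two windows.

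**Conclusion.** The mismatch is real and follows directly from the text: imaging is counted to day 30, while primary diagnoses are accepted to day 44 at the latest. Some scans that create primary events, and the negative scans from comparable work-ups, fall outside the outcome meant to reveal unequal testing. The check is truncated, not void, since all imaging to day 30 is still counted.

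The size is unknown. Under an assumed late share of 0% to 30%, it runs from no events to about 6 of roughly 22. Setting late events against the planned difference of about 12 might suggest a bias of that order. The documents give no basis for this: an event diagnosed late is not thereby a biased event, and nothing indicates that late imaging would differ by arm. Nor does the gap alter the primary test, the sample size of 666 or its power. The consequence is confined to how well ascertainment can be judged in a trial that is open after surgery. This is a low-cost improvement, not a flaw in the primary analysis.

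**What to change.** In sections 4a and 7c, define the surveillance-bias count as all symptom-prompted VTE imaging, positive or negative and including outside tests, done by day 30, plus any done within 2 weeks of a symptom report made at or before day 30. This matches the rule in section 4b. Record the date of the symptom report and of each test, using the results already to be forwarded under section 4a. Keep the day-30 count as a sub-total, and tabulate study-scheduled screening Duplex separately so that it does not mix with symptom-driven testing.

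The cost is a change of wording in two places and a few extra dates. The one real burden is requesting negative outside reports for the few patients referred late, which the post-day-30 contact rule in section 4b should be worded to allow. Sample size and power do not change.

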Specific aims: Does the use of perioperative pharmacologic agents (subcutaneous heparin; 5,000 units given before surgery and every 8 hours after surgery until discharge), compared to IPCs alone, for RP for prostate cancer:

1. Prevent the occurrence of symptomatic VTE following surgery? (primary efficacy outcome)
2. Increase the incidence of clinically significant lymphocele? (primary safety outcome)
3. Increase the incidence of clinically significant hematoma? (primary safety outcome)
4. Increase the incidence of major bleeding following surgery? (primary safety outcome)
5. Prevent the occurrence of any VTE (asymptomatic or symptomatic) following surgery? (secondary outcome)
6. Increase estimated blood loss during surgery? (secondary outcome)
7. Increase surgical drain output after surgery? (secondary outcome)

8. Lead to potential surveillance bias measured by increased or decreased use of diagnostic imaging for VTE relative to symptoms (e.g. lower extremity Duplex ultrasound, spiral CT angiography, V/Q scan, etc.)? (secondary outcome)

3. Background (briefly describe pre-clinical and clinical data, current experience with procedures, drug or device, and any other relevant information to justify the research)

An estimated 180,000 new cases of prostate cancer were diagnosed in 2016, and about 90,000 radical prostatectomies are performed in the United States annually [1-3]. Since the year 2000, a sharp change in practice patterns has shifted the traditionally open radical prostatectomy (RP) procedure to current practice where the great majority (likely >70%) are robotic-assisted laparoscopic RPs (RALRP) [3]. According to most guidelines, undergoing RP by any approach classifies a patient as high-risk for venous thromboembolism (VTE), including deep venous thrombosis (DVT) and pulmonary embolism (PE), and would lead to implementation of appropriate intermittent mechanical pneumatic compression devices (IPCs) and pharmacologic prophylaxis [4-8].

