An optional part of the study protocol, a subcohort of at least 200 patients (funds allowing) will be offered a routine 30-day post-RP screening lower extremity Duplex ultrasound to assess for DVT at Johns Hopkins for patients willing to travel to Johns Hopkins to obtain the ultrasound in this time frame. Patients are not required to obtain this screening ultrasound, but initial randomization will be stratified by whether patients opt to undergo ultrasound (and robotic vs. open surgery) to ensure study arms are balanced. In other words, patients willing to undergo ultrasound will be identified before randomization. All patients, regardless of whether they undergo ultrasound, will be assessed for all primary outcomes as described. For the subset of patients who obtain the ultrasound, it will be used to assess the secondary outcome of any VTE (asymptomatic or symptomatic). The outcome of any VTE will be tabulated based on the results of the screening ultrasound and any report of a symptomatic VTE episode (assessed by call at 30 days as described above). Stratified randomization is outlined in Figure 1. Written informed consent includes a plan to inform the patient and their primary physician of the results of the ultrasound and any incidental findings. Costs for the screening ultrasound obtained as part of the study will be covered by the study. Symptoms prompting a recommendation for evaluation to rule out DVT or PE (appropriate diagnostics/imaging to be determined by evaluating physician) will include:

1. Persistent unilateral or bilateral lower extremity edema
2. Persistent calf pain or cramping
3. Persistent or new chest pain
4. Persistent or new shortness of breath that started suddenly or worsens with exertion
5. Productive cough with bloody sputum
6. Fever and/or tachycardia without any known source of infection
7. Any other clinical concern for DVT or PE

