The primary efficacy outcome will be the incidence of symptomatic VTE within 30 days after surgery. A symptomatic VTE event will be defined as any imaging-confirmed VTE diagnosed after evaluation for VTE prompted by the presence of signs/symptoms concerning for VTE. The primary analysis will compare this rate between treatment arms at the 30-day follow-up for all patients. Symptomatic VTE will also include any deaths attributed to a clinically suspected VTE event without imaging confirmation (if autopsy is performed, VTE must be confirmed at autopsy; if autopsy is not performed, clinical suspicion of VTE as the cause will suffice). Symptoms prompting evaluation include:

1. Persistent unilateral or bilateral lower extremity edema
2. Persistent calf pain or cramping
3. Persistent or new chest pain
4. Persistent or new shortness of breath that started suddenly or worsens with exertion
5. Productive cough with bloody sputum
6. Fever and/or tachycardia without any known source of infection
7. Any other clinical concern for DVT or PE

The primary safety outcomes will include three separate measures of incidence of symptomatic lymphocele, incidence of symptomatic hematoma, or major bleeding within 30 days after surgery. Symptomatic lymphocele and symptomatic hematoma will include imaging confirmed events based on imaging pursued at the discretion of the primary attending urologist per routine practice (current routine practice involves imaging only if clinical symptoms suggest possibility of a lymphocele or hematoma). Events will be recorded regardless of the need for intervention (e.g. drain placement by interventional radiology). While screening studies show rates of 25-50% for postoperative lymphocele regardless of surgical approach (open or robotic), the rate of symptomatic lymphocele is thought to be around 10% or less [31,32]. Major bleeding will be defined as the need for transfusion of ≥ 2 units of packed red blood cells after the completion of surgery for anemia attributed to postoperative bleeding or need to return to the operating room for active bleeding.

c. Secondary outcome variables.

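### The any-VTE outcome omits a confirmed, symptom-free clot found on imaging done for another reason if the day-30 leg Duplex does not show it; the two rules for symptomatic VTE also need reconciling

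*Combined protocol and SAP*

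**What the plan says.** Aim 5 in Section 2 reads: "Prevent the occurrence of any VTE (asymptomatic or symptomatic) following surgery". Two places derive that outcome.

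- Section 4a: "The outcome of any VTE will be tabulated based on the results of the screening ultrasound and any report of a symptomatic VTE episode".
- Section 7c, on the asymptomatic part: "The asymptomatic VTE will be determined based on the results of the screening lower extremity Duplex ultrasound for asymptomatic DVTs". The overall rate is then "determined by adding the number of asymptomatic VTE events to the number of symptomatic VTE events experienced in the subcohort".

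The symptomatic part is the primary outcome. Section 7b defines it as "any imaging-confirmed VTE diagnosed after evaluation for VTE prompted by the presence of signs/symptoms concerning for VTE", and adds: "Symptomatic VTE will also include any deaths attributed to a clinically suspected VTE event without imaging confirmation". The symptom list in Sections 4a and 7b closes with a catch-all, "Any other clinical concern for DVT or PE". Section 4b has a further rule for this outcome, covering those with VTE symptoms reported by day 30 "who are diagnosed within 2 weeks of reporting symptoms (even if after the 30 day mark) will be included as symptomatic VTE events".

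Four other provisions bear on the point:

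- Section 7b expects imaging for suspected lymphocele or hematoma, at the attending urologist's discretion.
- Section 4a has the 30-day call document any postoperative VTE episode and its treatment.
- Section 11 has the screening scan done whatever earlier imaging showed.
- Section 7d confines the any-VTE analysis to patients who actually undergo the day-30 Duplex.

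**The concern.** The name of the outcome and aim 5 promise all VTE. The derivation is closed: an event must come from the screening leg scan or meet the definition of symptomatic VTE. Postoperative CT or ultrasound for a suspected collection is foreseen, and it can show a thrombosis that nobody was looking for. No rule gives such an event a category, so the written sum scores the patient as free of VTE even when the clot is confirmed and treated.

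At stake is the validity of a secondary outcome that rests on few events. A related issue touches the primary outcome. Section 7b makes the purpose of the evaluation part of the definition and Section 4b does not, so one record can be scored two ways.

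**Working it through.** **Step 1. Apply the written rules to typical subcohort records.** The imaging in every row was ordered for a reason other than VTE and falls within 30 days of surgery.

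| Record | Symptomatic, 7b | Symptomatic, 4b | Screening scan | Any VTE |
|---|---|---|---|---|
| Symptom-free PE on CT | No | No | Leg scan not expected to show it | **Omitted** |
| Symptom-free pelvic-vein clot on CT | No | No | Leg scan not expected to show it | **Omitted** |
| Symptom-free leg DVT, resolved on treatment by day 30 | No | No | Negative | **Omitted** |
| Symptom-free leg DVT, still visible at day 30 | No | No | Positive | Counted |
| Listed symptom reported by day 30, VTE diagnosed within 2 weeks, but the evaluation was not for VTE | No | Yes | Not needed | **Depends on which section governs** |
| Listed sign seen by staff but not reported by the patient | No | Unclear | Depends on site and persistence | **Unclear** |

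The first three rows are the defect. The fifth is the conflict between Sections 4b and 7b. The conflict is not confined to the subcohort, because it concerns the primary outcome.

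**Step 2. Check the population.** Section 7c sums events over the subcohort, that is, patients who agreed to the scan before randomization. Section 7d analyses only those who had it. A subcohort patient with a confirmed VTE who then misses the Duplex leaves the analysis altogether.

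**Step 3. Scale.** The planning rates are 5% and 1.5% (Section 7d). They reproduce the plan's power. A fixed one-sided test at 0.05 with 333 per arm gives 81.8%. A three-look simulation with one-sided p-value limits 0.001, 0.015 and 0.048 and the interim futility limits gives 82.4%. The plan states 82%.

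The subcohort is 200 (Section 7a), so about 100 per arm. If the same rates apply there:

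- Expected symptomatic events: 100 × 0.05 + 100 × 0.015 = 5 + 1.5 = 6.5.
- One omission relative to these: 1/6.5 = 15%. Two: 2/6.5 = 31%.

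Any VTE also includes screening-detected DVT, so these percentages are too high for it. The two screening studies in Section 3 found 2/245 and 18/109. Both scanned early after surgery rather than at day 30, so they give only a rough range:

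- 200 × 2/245 = 1.6, total 6.5 + 1.6 = 8.1. One omission is 1/8.1 = 12%.
- 200 × 18/109 = 33.0, total 6.5 + 33.0 = 39.5. One omission is 1/39.5 = 2.5%.

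The documents give no rate of incidental VTE. As an assumption only, suppose 5–10% of patients have such imaging and 5–15% of those studies show a clot. That is 200 × 0.05 × 0.05 = 0.5 to 200 × 0.10 × 0.15 = 3 clots in the subcohort, before subtracting those that the Duplex finds again.

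**Step 4. Direction.** Suppose, again as an assumption, that imaging is done in 5% of controls and 10% of heparin patients, with a 10% yield in controls. Per 100 patients, controls lose 100 × 0.05 × 0.10 = 0.5 events. Leaving screening-detected DVT aside:

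- *Same yield under heparin:* it loses 100 × 0.10 × 0.10 = 1.0. The full counts are 5.5 and 2.5 (difference 3.0, ratio 0.45). The counted events are 5.0 and 1.5 (difference 3.5, ratio 0.30). Both scales move toward heparin.
- *Yield reduced by the planned ratio, 1.5/5 = 0.3:* heparin loses 100 × 0.10 × 0.03 = 0.3. The full counts are 5.5 and 1.8 (difference 3.7, ratio 0.33). The counted events are again 5.0 and 1.5 (difference 3.5, ratio 0.30). The difference now moves against heparin and the ratio slightly toward it.

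The sign depends on unknown imaging rates, unknown yields and the effect scale.

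**The case against.** The strongest defence is that limiting asymptomatic events to the screening scan is deliberate and sound. Under Section 4c treatment is open after surgery, while the scan is performed and read blinded. It is also scheduled alike in both arms. Clots found on discretionary imaging are open to unequal detection. This stands as a reason to keep symptom-free incidental clots out of the primary outcome and to show any VTE without them. It does not justify scoring a confirmed clot as no VTE under aim 5.

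A second defence is that little is lost: the 30-day call documents any VTE episode, and the scan is done regardless of earlier imaging. That is correct for a leg DVT that persists. For the rest, the event is recorded but no rule classifies it.

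A reader might go further and infer that the primary outcome drops VTEs in patients with listed symptoms. Section 7b alone could be read that way, but Section 4b counts patients who report symptoms by day 30 and are diagnosed within two weeks, without asking why the scan was ordered. Sections 4a and 7b also make the listed symptoms themselves a trigger for VTE evaluation, with a catch-all. Section 4b does say that contact after day 30 serves to confirm events due to symptoms or found on screening, but that sentence governs contact and does not define the outcome. What remains is a conflict between two rules, not an established loss.

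**Conclusion.** The gap in any VTE is real and follows from the text of Sections 4a and 7c. It is limited to subcohort patients with a confirmed VTE, no VTE symptoms, and a clot that the day-30 leg Duplex does not show. Section 7d widens it slightly by excluding those who miss the scan.

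Its size cannot be derived from the documents. With about 6.5 symptomatic events expected, assuming the planning rates hold in the subcohort and allocation is equal, one or two omissions would be noticeable. They would weigh less if screening finds many DVTs.

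Two stronger conclusions might be inferred and are not supported. One is that the omission favours heparin; Step 4 shows that the sign turns on assumptions and on the effect scale. The other is that 8–46% of events are lost. That comes from dividing the assumed 0.5–3 clots by 6.5, which leaves out screening-detected DVT and ignores clots still visible at day 30.

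The difference between Sections 4b and 7b should be settled before any event is classified. The sample size is unaffected, because the correction does not add symptom-free clots to the primary outcome.

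**What to change.** 1. In Sections 7c and 4a, define any VTE in the subcohort as any DVT or PE confirmed by imaging or autopsy within the outcome window, whatever prompted the imaging, plus the screening result. Keep the existing provision for VTE-attributed deaths.
2. In Section 7d, do not drop a subcohort patient with a confirmed VTE because the day-30 Duplex was not done.
3. Merge Sections 4b and 7b into one rule for symptomatic VTE. It should say whether a listed sign or symptom present before the imaging is enough when the test was ordered for another suspected diagnosis, whether signs noted by staff count as reported, and how the two-week extension applies. Symptom-free incidental clots stay out of the primary outcome.
4. Record the indication for each scan alongside the type and frequency already planned, and classify events blinded to arm.
5. Report any VTE with and without incidental events.

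The cost is protocol wording, one field on the event form and one extra tabulation, with no added procedure. The downside is that incidental clots may be detected unequally if imaging for other reasons differs by arm. The paired analysis in item 5 and the imaging comparison under aim 8 would show this.
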